The primary endpoint is the difference in VAS score applied after CME and after SCS compared to the VAS score applied at baseline assessment before spinal cord stimulation. It is assumed that SCS will achieve a 2.4 point reduction in VAS compared to CME, according to previous information ⁴⁴.

c) Intended applications and performance of the product under investigation

The Medtronic® spinal neurostimulation system with EVOLVE flow programming is indicated for the pain treatment of failed back surgery syndrome and has all the elements for its application.

d) Risks and expected adverse effects of the product

See section A4

A.6 CLINICAL RESEARCH DESIGN

A.6.1 General

This is a prospective study, randomized to two modes of spinal cord stimulation control (CS) and experimental (EME), single-blind and crossover.

Patients will be included in the study by randomizing the spinal cord stimulation mode after signing the informed consent form and verifying that they meet all the inclusion criteria and none of the exclusion criteria. Randomization will be performed by telephone call to the central randomization center, which will assign the patient stimulation mode according to the randomized list.

The devices are delivered to the investigators duly manufactured and labeled and are deposited in the centers where they will comply with the appropriate maintenance and conservation conditions. The centers chosen to carry out the study have sufficient means and proven experience in the handling and maintenance of the devices.

A.6.2 Product under research and testing

In this study, the conventional spinal cord stimulation method (EMC limb) and the experimental 1 KHz spinal cord stimulation method with the EVOLVE programming guide (EME limb) will be used in the same patient after a washout period, randomizing the patient to start with one limb or the other. Randomization will be performed

telephonically by contact between the principal investigator and the central randomization center located at the CRO. It is planned to act in accordance with clinical practice in these patients, providing at all times what is necessary for the perfect treatment of the patients according to the knowledge and training of the professionals involved in the clinical research.

A.6.3 Participants

The criteria for the selection of the participant subjects are as follows.

.- Inclusion Criteria

Patients over 18 years of age.

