The electrode(s) is (are) placed. A single neurostimulator per patient (device). The patient is then randomized to one of the two modes of spinal cord stimulation EMC or EME, by telephone call, and an appointment is made for visit 3. Adverse effects and tolerability of the system (rejection, infection or migration) are assessed. A first 2-day washout period is initiated.

.- Visit 3 (day 0)

The first period of spinal cord stimulation begins with the branch to which the patient has been randomized: EMC or EME. If the patient has been assigned to the EMC control group, after mapping the search for the pain area, the neurostimulator is programmed to conventional stimulation with paresthesia at 60 Hz and a pulse width between 300-450 μ s. If the patient has been randomized to the EMC experimental group, after mapping the search for the pain zone, stimulation is programmed at 90% of the subthreshold with a pulse width of 90 μ s and frequency of 1000 Hz, placing the bipole in the T9-T10 space. The patient is asked if there have been any complications since electrode insertion (s).

.- Visit 4 (day 5)

VAS and OC scale are performed. The device is examined and questioned for possible adverse effects and tolerability of the system (rejection, infection or migration). The device is then deprogrammed and a second 2-day washout period is initiated.

.- Visit 5 (day 7)

Possible adverse effects and tolerability of the system (rejection, infection or migration) are questioned. The programming of spinal cord stimulation is started again, so that the patient is administered the MCE if he/she had received the MES, and vice versa.

.- Visit 6 (day 12)

The VAS and OC scale are performed. The device is re-examined and possible adverse effects and tolerability of the system are questioned. A final decision is made to implant or remove the device.

.- Visit 7 (4 weeks after final implantation/withdrawal of system)

The VAS and OC scale are performed. The device is re-examined and questioned for possible adverse effects and tolerability of the system.

A.6.5 Monitoring plan

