The study will be monitored by personnel specifically contracted from a company external to the promoter, and an in-person visit will be made at the start, an intermediate visit, and a final visit at each participating center. At the beginning of the study, the first visit will be made, during which all aspects of the study will be explained to the research staff, the informed consent procedure will be explained, the protocol will be reviewed, the way in which patient data will be collected, the responsibilities of the researcher, the dispensing and maintenance of the samples and all related issues. Telephone follow-up will be provided to the centers throughout the duration of the study.

The monitor will have access to both paper and computerized medical records and will ensure that patient data are properly collected and stored in the investigator's file for the time required by current regulations.

The monitor will be informed of adverse events occurring during the clinical investigation through the investigator at each center and will report serious and related events to the authorities within the established time limits.

Evaluation	Visit 1 Basal	Visit 2	Visit 3 End of washing	Visit 4 EMC or EME	Visit 5. End of washing	Visit 6 EMC or EME	Visita 7
DAY of the study	-3 *	-2	0	5	7	12	40±2
Selection Criteria Evaluation	X						
Explanation of study and signature of consent	X						
Clinical data collection	X						
Randomization		X					
VAS	X			X		X	X

Oswestry Questionnaire	X			X		X	x
Temporary electrode implant without stimulus		X					
Start of spinal cord stimulation according to randomization A or B (day 3)			X		X		
System tolerability		X	X	X	X	X	
Adverse effects		X	X	X	X	X	x
Subsequent follow-up							x

(*) window of -2 days with respect to Visit 3.

A.7 STATISTICAL CONSIDERATIONS

This is a multicenter, controlled, randomized (spinal cord stimulation method: EMC or EME), crossover and single-blind study.

First, a descriptive analysis of the study variables will be performed, calculating the absolute and percentage frequency (n and %) of each category in the qualitative variables; in the quantitative variables, we will first study whether they fit the Gaussian distribution by applying the Kolmogorv-Smirnov goodness-of-fit test to the "Normal" distribution, showing the means and standard deviations if yes, and the medians and 25th and 75th percentiles if no, and if no, the medians and 25th and 75th percentiles.

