In order to respond to the main objective of the study, two variables will be calculated for each patient that reflect the difference between the initial VAS minus the final VAS, one for each type of stimulation (EMC or EME). We will calculate whether these differences conform to the Gaussian distribution. If they fit the "Normal" distribution, the means with their standard deviations will be calculated for each of them, with the Student's t-test for paired samples to study if this difference is statistically significant, these means will be adjusted for age and sex, establishing the possible statistical differences with a general linear model of repeated measures. In the case of not obtaining distributions that fit the "Normal", the medians and the 25th and 75th percentiles will be calculated, obtaining the possible statistical differences by applying the Wilcoxon test.

For the objective of estimating the proportion of patients with a minimum decrease of 50%, it will be calculated in each case which patients meet this condition, calculating the percentage of patients in each type of stimulation, and studying the possible statistically significant differences with the Mc Nemar test.

The disability associated with pain will be evaluated with the descriptive statistics already mentioned and for each moment of the study and in each type of stimulation.

Variables will be created with the differences between the initial and final quality of life scores, studying their differences with the same parameters and tests discussed for the differences in VAS.

The absolute and relative frequencies (%) of each of the adverse effects found in the follow-up will be calculated as a safety study, in the total of the study and for each type of stimulus. Possible differences will be studied with the Mc. Nemar test.

A statistical significance level of $p < 0.05$ is considered, thus establishing a safety level of 95%.

All analyses will be performed with SPSS software version 24.0 (IBM Corp. Released 2016. IBM SPSS Statistics for Windows, Version 24.0. Armonk, NY: IBM Corp.)

Sample size

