The main objective of the study is to establish a mean difference in the decrease in VAS. Based on this, we estimate a difference between the two methods of spinal cord stimulation (EMC and EME) of 1.9 points, in agreement with previous data in the medical literature,⁵⁵ with standard deviation of 3.2 and 2.0, assuming a Spearman correlation between both values of 0.5 (minimum). Using the formula for paired mean difference, for a confidence level of 95% and a statistical power of 80%, 19 patients who meet the inclusion criteria and do not meet any exclusion criteria are required, calculating a loss rate of 20%, 24 patients are expected to be included in the study.

A.8 DATA MANAGEMENT

A clinical research data collection form (CRF) will be created, where each investigator will collect the data of each patient participating in the study.

In agreement with the scientific committee, minimum and maximum values will be established for each variable of the CRF, creating validation rules and messages to the user communicating the validation rule that is not being complied with, as well as input masks for the variables that require it, such as dates. It will be possible to proceed to fill the CRF in successive times, with the consequent saving at each moment.

A.9 AMENDMENTS

The Investigational Product, Protocol, CRF, informed consent or other subject information, or other clinical investigation documents may be amended during the clinical investigation if necessary. In this case a justification statement will be included with each amended section of a document. Proposed amendments to the Protocol will be agreed between the sponsor and the coordinating investigator. They should be notified to and approved by the CEIM and regulatory authorities if required and the version number and date of the amendments will be documented.

For non-substantive changes that do not affect the rights, safety, and welfare of human subjects and are not related to the objectives or endpoints of the clinical investigation, notification to CEIM and, where appropriate, to regulatory authorities will be sufficient.

A.10 DEVIATIONS FROM THE CLINICAL RESEARCH PLAN

Reports of deviations will be communicated to CEIM, if the deviation affects the rights, safety and welfare of the subjects or the scientific integrity of the clinical investigation. In such cases, written approval will be obtained from CEIM.

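### The crossover is analysed as simple matched pairs: no planned test in A.7 has a period or sequence term, so any period effect enters the EME–EMC estimate or its error variance

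*Combined protocol and SAP*

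**What the plan says.** Section A.6.2 gives both modes to every patient, "randomizing the patient to start with one limb or the other". At Visit 5 (section A.6.4) the modes are exchanged, "so that the patient is administered the MCE if he/she had received the MES, and vice versa" (the translation varies the abbreviations for EMC and EME). This is a two-sequence, two-period crossover with VAS readings at Visit 4 (day 5) and Visit 6 (day 12).

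Section A.7 forms two variables per patient, baseline VAS minus final VAS, one for each mode. If these look normal, they are compared with a "t-test for paired samples to study if this difference is statistically significant", and "these means will be adjusted for age and sex, establishing the possible statistical differences with a general linear model of repeated measures". If not, the Wilcoxon test is used. Responder proportions are compared by "studying the possible statistically significant differences with the Mc Nemar test", adverse effects also by McNemar, and the disability (quality-of-life) score differences by the same tests as VAS. Period, sequence and order appear in none of these tests, nor in the sample-size formula. Section A.6.1 mentions a randomised list but gives no ratio or blocking. The documents contain no separate SAP.

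**The concern.** A paired test labels each reading by mode and discards the period in which it was taken. In a crossover, half the patients or so have EMC first and the others have EME first, so any change over time that is common to both modes pushes the within-patient difference in opposite directions in the two sequences. If the sequences are unequal among completers, part of that change appears as a treatment effect. If they are equal, it cancels in the mean but stays in the standard error. Age and sex are between-patient covariates and cannot absorb it.

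A change over time is plausible here. The schedule places "Temporary electrode implant without stimulus" at Visit 2 (day −2), so the two readings fall 7 and 14 days after an invasive procedure. The documents neither state nor rule out such a change.

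The trial is sized at almost exactly 80% power and has no reserve to absorb a larger error variance.

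**Working it through.** **Inputs from the Sample size paragraph of A.7.** Difference 1.9; SDs 3.2 and 2.0; correlation 0.5, described there as a minimum; 95% confidence; 80% power; 20% loss.

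**Reproducing the plan's figure.** SD of the paired difference = √(3.2² + 2.0² − 2 × 0.5 × 3.2 × 2.0) = 2.80. With two-sided 5% alpha, n = ((1.960 + 0.842) × 2.8/1.9)² = 17.05. Adding the small-sample correction z²/2 = 1.92 gives 18.97, so 19. Exact power at n = 19 is 79.9%. 19/0.8 = 23.75, so 24. The plan's 19 and 24 are right for a paired test with no period effect.

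**Effect of a period change.** Both change scores use the single Visit 1 VAS, so it cancels and the tested variable is D = VAS(EMC) − VAS(EME). Suppose VAS falls by p between Visit 4 and Visit 6 whatever the mode. Then D has mean δ + p in the n1 EMC-first completers and δ − p in the n2 EME-first completers. With n = n1 + n2:

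- bias of the paired mean = p(n1 − n2)/n
- expected variance of D = SD² + 4p²·n1·n2/(n(n − 1))

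Example at 10:9 and p = 2: bias = 2 × 1/19 = 0.11; variance = 7.84 + 16 × 90/(19 × 18) = 7.84 + 4.21 = 12.05, which is 1.54 times the planned variance.

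**Simulation.** p is assumed, over the range 0 to 3. D is normal with SD 2.8, and there are 19 completers. The planned test is a one-sample t on D (18 df). The adjusted test uses the unweighted mean of the two sequence means of D with the pooled within-sequence variance (17 df).

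Bias and type I error by completer split:

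| Split | Bias per point of p | Planned type I error, p = 2 | Adjusted |
|---|---|---|---|
| 10:9 | 0.05 | 1.8% | 5.0% |
| 11:8 | 0.16 | 3.0% | 5.0% |
| 12:7 | 0.26 | 5.5% | 5.0% |
| 13:6 | 0.37 | 10.3% | 5.0% |

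At 10:9, planned power for p = 1.5, 2 and 3 is 75, 70 and 54% if the odd patient is EMC-first, and 67, 58 and 37% if EME-first. Adjusted power is about 79.5%. The mean 95% CI half-width is 1.42 at p = 1 and 1.65 at p = 2 as planned, against 1.34 adjusted.

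**Averaging over likely splits.** The documents do not say how the list is built, so two cases are shown. A 12:12 list with five random losses gives 10:9 with probability 2 × C(12,2) × C(12,3)/C(24,5) = 29,040/42,504 = 68%, 11:8 with 28% and 12:7 with 3.7%; 13:6 cannot occur. An unblocked list of 19 gives 13:6 or worse with probability 17%.

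| p | Planned power, 12:12 list | Planned power, unblocked list |
|---|---|---|
| 0 | 79.9% | 79.8% |
| 0.5 | 78.9% | 78.6% |
| 1 | 75.8% | 75.1% |
| 1.5 | 70.5% | not shown |
| 2 | 63.5% | 62.2% |
| 3 | 45.9% | 47.1% |
| Adjusted test, any p | 79.2% | 77.2% |

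Averaged type I error of the planned test falls from 5.0% to 1.0% across this range with the 12:12 list and stays near 5% with the unblocked list. The adjustment gains power on average once p exceeds about 0.45 (12:12) or 0.7 (unblocked).

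**If the correlation exceeds its stated minimum (averaged over the 12:12 list).** At r = 0.6 (SD 2.56), planned power is 82.3, 77.0 and 69.4% at p = 1, 1.5 and 2, against 85.8% adjusted. At r = 0.7 (SD 2.30), it is 84.0 and 76.2% at p = 1.5 and 2, against 92.1% adjusted.

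**The case against.** The strongest reply is that the harm depends on a quantity the documents do not supply. Section A.4 lists complications of the implant but does not name procedural pain that resolves over these days, and the upper values of p exceed the assumed treatment effect of 1.9. The shared baseline cancels, so regression to the mean from the VAS entry threshold of 7 is weak support for a change between Visit 4 and Visit 6. At modest p the planned test does well, and with an unblocked list it has more power than the adjusted test until p is about 0.7. Averaged over either list, its type I error does not rise materially above 5%; the 10.3% figure needs both a 13:6 split and p = 2. If the correlation is above 0.5, the 80% target is still met at p = 1. No binary scenario was calculated for the McNemar comparisons, and with 19 pairs the discordant counts may be sparse.

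All of this stands, and it limits the weight of the point: this is not a general false-positive problem, and the size is conditional. It does not remove the omission. No section supplies a period or sequence term. Balance among completers is not assured either: the list is undescribed, randomisation is at Visit 2, and section A.6.3 withdraws patients on mapping and paresthesia results, which can follow allocation.

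**Conclusion.** The concern holds. A.7 analyses a randomised two-period crossover without its period structure, and this applies to every planned comparison of the modes. Near balance the consequence is a conservative test with a wider interval. On a 12:12 list, the loss against the adjusted test is 79.2 − 75.8 = 3.4 power points at p = 1 and 79.2 − 63.5 = 15.7 at p = 2. Bias and excess type I error become clear only at a marked imbalance. At p of about 0.5 or less the effect is minor.

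These sizes rest on an assumed p, normal differences without the limits of a 0–10 scale, the plan's SDs with r = 0.5, and 19 completers lost at random. The point should be fixed because the fix is cheap; it does not invalidate the design. Confidence in its practical importance is medium, because p is unknown.

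**What to change.** Amend A.7 so that the primary VAS analysis accounts for period. The smallest edit is to add sequence as a between-subject factor to the repeated-measures model already named; the mode-by-sequence term is then the period effect. Equivalent choices with complete pairs and no further covariates are:

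- a linear mixed model on the Visit 4 and Visit 6 VAS, with mode, period and sequence fixed and patient random;
- a two-sample t-test between sequences on within-patient period differences.

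On one simulated data set, the mixed model and the repeated-measures model gave the same estimate (1.628) and standard error (0.5405), and the sequence-contrast t-test gave the same t as the repeated-measures model (3.012). State which one is primary, and report EME minus EMC with its 95% CI.

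For non-normal data, use the rank-sum test between sequences on period differences. For the paired binary comparisons, use a period-adjusted test (Mainland–Gart, or conditional logistic regression with period), bearing in mind that discordant pairs may be few. Apply the same approach to the disability score.

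The cost is a wording amendment under section A.9, where amendments are handled as follows: "They should be notified to and approved by the CEIM and regulatory authorities if required". It uses one degree of freedom and needs no new patients, visits, data or change to randomisation. If there is no period effect, the power cost is about 0.4 points at 10:9, 1.3 at 11:8, 3.2 at 12:7 and 6.2 at 13:6, or on average 0.7 (12:12 list) or 2.6 (unblocked list). A period term does not address carry-over, which is a separate question.

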Regarding the moment of inclusion, it will be one day before the placement of the electrode(s) and three days before the beginning of the spinal cord stimulation, once it has been verified that they meet all the inclusion criteria and none of the exclusion criteria. The patients will be included in the study in a randomized manner, after they sign their voluntary participation in the study before any type of intervention is performed, for which they will be duly informed through the patient information sheet and the oral explanation provided by the researcher or authorized collaborator. Randomization will be carried out by telephone through contact between the principal investigator and the central randomization center of the CRO.

The expected duration of the clinical investigation is 16 months of recruitment in each center, plus 15 days of study and 1 month of patient follow-up, and will be maintained until the number of patients foreseen in the sample size described is reached.

The duration of each patient in the study will be 15 days from the day on which the study scales (VAS and quality of life) are performed at the baseline visit, plus 1 month of subsequent follow-up.

Twenty-four patients will be selected who meet the inclusion criteria and do not meet any exclusion criteria, calculating a loss rate of 15%-20%, it is expected that 19-20 patients will be included in the study.

The inclusion period has been estimated at 16 months for each center.

A.6.4 Procedures

The participants who take part in the clinical research follow the following procedures throughout the study. They are selected at the medical visit and once it has been verified that they meet all the inclusion criteria and none of the exclusion criteria and their possible participation in the study has been decided, their participation in the study is proposed to them by explaining the patient information sheet and signing the informed consent form. From that moment on, at visit 1 (which can be the same visit or a previous one, provided that no procedure related to the study is performed until the consent form is signed), the mode of spinal cord stimulation to be applied to the patient is randomized, with a single device for each patient, and the study procedures will be performed. Randomization will be performed by telephone contact to the central randomization center of the CRO.

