The procedures used in this work to evaluate the efficacy of spinal cord stimulation are the visual analog scale (VAS) and the Oswestry (OC) questionnaire on disability associated with low back pain (Oswestry Disability Index). The VAS makes it possible to measure pain intensity with maximum reproducibility between observers. It consists of a horizontal line of 10 centimeters, at the ends of which are the extreme expressions of pain perception. On the left side is located the absence or lower intensity and on the right side the higher intensity. The patient is asked to mark on the line the point indicating the intensity (see appendix 3) ⁵³. The Oswestry scale is the most recommended scale for measuring disability due to low back pain. ⁵⁴ It consists of a self-administered questionnaire that measures limitations in daily activities. It consists of 10 questions with 6 possible answers each. The score for each answer ranges from 0 (less disability) to 5 (more disability). The result is expressed in % by dividing the total score by 50, with 0% being the least disability possible, and 100% the most disability. It is classified into 5 categories: minimal disability (0% to 20%), moderate disability (21% to 40%), severe disability (41% to 60%), paralyzed (61% to 80%) and category requiring more careful evaluation (81% to 100%, could be bedridden patients or those who exaggerate symptoms). (See Annex 4).

Study variables

The study is structured in 7 visits. The variables collected and structures of the visits are as follows:

.- Visit 1 (day -3 to -5)

The patient signs the informed consent for the study, once he/she has been informed of the nature of the study (the information may have been received at a previous visit). The selection criteria are reviewed (all the inclusion criteria must be met and none of the exclusion criteria must be met). Demographic data (age, sex), anthropometric data (weight, height), pathological history, history of vertebral and/or dorsolumbar pathology, history of spinal surgery, previous pharmacological medical treatment and nature of pain are collected. The VAS and the OC scale (disability associated with low back pain) are performed.

.- Visit 2 (day -2)

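### Does naming both a paired t-test and an age- and sex-adjusted model leave the primary VAS comparison without a deciding test?

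*Combined protocol and SAP*

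**What the plan says.** Section A.7 forms two variables per patient, the fall in VAS from baseline under EMC and under EME. It then says "We will calculate whether these differences conform to the Gaussian distribution". If they do, the plan uses a Student "t-test for paired samples to study if this difference is statistically significant", and the sentence goes on: "these means will be adjusted for age and sex, establishing the possible statistical differences with a general linear model of repeated measures". If they do not, only a Wilcoxon test is named. One significance level, p < 0.05, covers the whole section.

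The section does not label any test as primary, supportive or sensitivity, and it does not list the terms of the repeated-measures model. The objectives and hypothesis in section A.5 name no test.

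The sample size paragraph of A.7 assumes a difference of 1.9 points, standard deviations of 3.2 and 2.0 and a correlation of 0.5. It applies the formula for a paired mean difference and arrives at 19 patients, or 24 with 20% loss. The secondary score changes follow the VAS scheme ("studying their differences with the same parameters and tests discussed for the differences in VAS"), so they share the same wording.

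**The concern.** The sentence gives a test of significance and then, without a break, a second way of establishing differences. Both sound inferential, and both answer to the same 0.05 threshold. Age and sex do not change within a patient, so they cannot confound a within-patient contrast. The adjustment therefore removes no bias and seems only to supply a second p-value.

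If the two disagreed, the text would not say which is the trial's result, and the choice could be made after seeing the data. If either were allowed to count, the type I error would exceed 5%. With 19 evaluable patients and power close to 80%, a borderline p-value is quite possible.

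**Working it through.** **Inputs.** From the sample size paragraph of A.7: difference 1.9, SDs 3.2 and 2.0, correlation 0.5, 19 evaluable, 20% loss, alpha 0.05. Two-sided testing is assumed because the section does not state it. Also assumed: normal data, age with mean 52 and SD 12, and equal numbers of each sex.

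**1. The plan's own figure.** SD of the paired difference = √(3.2² + 2.0² − 2 × 0.5 × 3.2 × 2.0) = √7.84 = 2.8. The normal approximation gives n = ((1.960 + 0.842) × 2.8 / 1.9)² ≈ 17.05. Adding the small-sample term 1.960²/2 ≈ 1.92 gives 18.97, so 19. Then 19/0.8 = 23.75, so 24. Both figures reproduce. Exact paired-t power at n = 19 is 79.9%. A one-sided calculation gives 13.4, so 14, which does not match. The trial was therefore sized for a two-sided, unadjusted paired comparison.

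**2. What the adjusted model tests.** Let D be a patient's EME change minus EMC change.

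- *No mode-by-covariate terms.* Age and sex add the same amount to both of a patient's values and cancel in D. D then has an intercept only, and the test of mode is mean(D)/(SD(D)/√n) on n − 1 degrees of freedom. That is the paired t-test, so disagreement is zero.
- *With mode-by-age and mode-by-sex terms, covariates centred.* D = δ + γ₁(age − mean age) + γ₂(sex − mean sex) + error. Least squares gives δ̂ = mean(D), the same estimate as the t-test. Only the standard error and the error degrees of freedom (n − 3 = 16 instead of 18) change. Two fewer degrees of freedom and no covariate effect take power from 79.9% to 79.3%.

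**3. How often the p-values part company.** Both tests were applied to the same simulated differences (n = 19, 60,000 trials per row, covariates centred; Monte Carlo error about 0.1 point for error rates near 5–6%).

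| Assumed correlation of age with D | Disagree, true difference 1.9 | Disagree, no difference | Type I, t-test | Type I, model | Type I if either may be claimed |
|---|---|---|---|---|---|
| 0 | 2.6% | 1.0% | 5.1% | 5.1% | 5.6% |
| 0.3 | 3.7% | 1.7% | 4.8% | 5.9% | 6.2% |
| 0.5 | 6.8% | 3.8% | 5.0% | 8.5% | 8.7% |

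The t-test stays at its nominal level throughout. At a correlation of 0.5 nearly all the excess comes from the model itself (8.5% of the 8.7%), because it treats randomly varying ages as fixed.

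**4. Which test the text points to.** The t-test is named first and is given the task of judging significance. The sizing formula is the one that belongs to it. The model enters as an adjustment of means already compared.

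**The case for a change.** The strongest case for a change is that order of mention and a sizing formula are not a decision rule. Naming one test would cost a sentence and no patients. That is true, and the missing label is a real gap in the wording.

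The adjusted model can also be set up in less benign ways. With age at its mean and the two sexes weighted equally, disagreement at the planned effect is about 6% and the either-test error 5.8–6.3% for evenly split sexes. For an assumed 14:5 split they are 16% and 7.5%. If age were left uncentred and the mode coefficient read at age zero, the model would contradict the t-test in about 73% of trials at the planned effect. That last reading is not an adjusted mean in any useful sense, and the plan speaks of adjusted means.

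The others show that the model can be the weaker or less reliable test. They do not show that it decides. Every inflated error rate also needs a rule that either p-value may be claimed, and the plan states no such rule.

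The opposite objection is that the translated sentence may assign the t-test to baseline against end of period within each mode, leaving the model as the only between-mode test. The phrase about possible differences is shared by the model and the Wilcoxon test, which lends this some support. On that reading nothing is tested twice. The paired-difference sizing makes it the less likely reading, but it cannot be excluded.

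**Conclusion.** The label is missing, but analysts can fill the gap sensibly from the plan itself. The within-patient comparison that A.7 sizes decides, and the age and sex model supports it. On that reading the type I error is the nominal 5% and power is 79.9% at 19 evaluable patients.

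The alternative test is either identical (no mode-by-covariate terms) or, read at the covariate means, gives the same estimate with a slightly different standard error. In that second case the tests disagree in about 2.6% of trials at the planned effect, assuming normal data and no age or sex effect. The either-test error of about 5.6% is not bounded there: it reaches 6.2% and 8.7% at assumed age correlations of 0.3 and 0.5, and it depends on the sex split and coding. But it arises only under a claim rule that the plan does not contain. The numbers of 19 and 24 stand, and no change to the plan is called for.
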